settings (12, 14, 19). Therefore, identifying patterns and predictors of LPV compliance in a Canadian context through our study may help inform the design of educational efforts and systemic changes to tackle areas of deficiency.

3. Research question

Primary research question: In patients undergoing general anesthesia with an endotracheal tube for non-cardiac surgery, what is the compliance rate to LPV in Fraser Health Authority, and predictors of such compliance?

Secondary research questions: What are time trends and shifts in LPV compliance from the pre-COVID to the post-COVID era? Are these trends sustained into the “new normal” era?

4. Research objectives and hypothesis

The objectives for this study are to:

1. Identify rates of compliance with LPV guidelines in the Fraser Health Authority in the Province of British Columbia, Canada. Compliance with ventilation guidelines is defined as meeting two criteria. The first is that their average tidal volume is 6-8 mL/kg IBW and the second is that the average positive end expiratory pressure (PEEP) is at least 5 cm H₂O. Patients ventilated according to one or neither of the above criteria will not be considered to have been ventilated according to the guidelines.
2. To elucidate predictors of compliance with LPV practice among providers. These predictors may help inform the design of educational efforts and systemic changes to tackle areas of deficiency.
3. To elucidate time trends and shifts in LPV compliance from the pre-COVID pandemic to post-pandemic era.
4. To evaluate whether time trends and shifts in LPV compliance through the pandemic are sustained.

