Physiologic and therapy data: Data obtained from the CPA data warehouse will include all data from the anesthesia monitor (e.g., heart rate, oxygen saturation, and MAP) and ventilator (e.g.: tidal volume, end tidal carbon dioxide (EtCO₂), and end tidal inhalational gas concentrations) as well as any data entered manually (medications, procedures). The primary variables of interest include respiratory rate, set and exhaled tidal volume, peak pressure, PEEP, non-invasive and invasive blood pressures including systolic, diastolic and mean arterial pressures, heart rate, inspired oxygen, oxygen saturation, and end-tidal CO₂ and volatile gas measurements. All data will be extracted as averages during “total surgical monitoring time” (see Appendix for details). FiO₂ values will be restricted to values between 21-100% and SpO₂ values will be restricted to values between 70-100% prior to calculating averages. PEEP data will be limited to values between 0-15 mmHg. If data is missing at a given timestamp it will be excluded from the analysis. Measured average tidal volume will be compared to LPV tidal volume based on IBW as calculated by the patient’s height. Patients will be deemed to have been ventilated according to a lung protective strategy if their average tidal volume was 6-8 mL/kg IBW and their average PEEP throughout the case was as least 5 cm H₂O. Date of surgery will also be extracted to facilitate plotting of the Shewhart chart, and determination of pre-COVID/COVID era status (see section 7 Statistical Plan). Time of surgery start will be extracted to determination of night/weekend shift status.

Measures

Baseline demographics for all study patients include age, sex, height, weight, smoking status in the last year, and ASA classification. Data relating to the surgery includes the date of surgery, hospital admission date, hospital discharge date, if the surgery was elective or emergency, a common procedural code used to identify the type of surgery, and duration of the procedure.

To determine “compliance to LPV”, the response variable of our prediction model, tidal volume per unit of body weight in kilograms will be calculated and compared to the guidelines. Average PEEP will be calculated in cm H₂O and compared to the guidelines. The average tidal volume will be calculated in mL throughout each case. IBWs will be calculated using height according to the Devine formula²⁹:

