$$\text{Ideal body weight (IBW) (men)} = 50 \text{ kg} + 2.3 \text{ kg} \times (\text{height (inches)} - 60)$$

$$\text{Ideal body weight (IBW) (women)} = 45.5 \text{ kg} + 2.3 \text{ kg} \times (\text{height (inches)} - 60)$$

7. Statistical plan

Software

Microsoft Excel (Microsoft Corporation, Redmond, WA), R Console (R Foundation for Statistical Computing, Vienna, Austria), Anaconda Navigator Distribution (python), and SAS Base 9.4 statistical analysis software will be used for analysis.

Part I: Patterns of compliance to LPV and relationship with default ventilator settings

- Descriptive statistics for proportion compliance to LPV will be calculated for the entire dataset
- Among the non-compliance cases, the % attributable to the following will be calculated. This analysis is useful for determining areas of intervention/education required:
 - Low PEEP
 - Inappropriate (both too high or too low) tidal volume
 - Too low tidal volume
 - Too high tidal volume
 - Both low PEEP and inappropriate tidal volume
- Using the entire data set, for tidal volumes from 400-600mL, we will plot the % of patients in whom that tidal volume satisfies LPV criteria. This will inform any required change to the default tidal volume ventilator setting to maximize the number of patients satisfying LPV criteria if the tidal volume setting were left unchanged.
- We will model improvements in LPV compliance if the default PEEP setting on anesthesia machines were changed from PEEP = off to PEEP = 5.

Part II: Investigation of time trends to compliance

A Shewhart control chart (p chart) of LPV compliance each month will be presented to investigate time trends of LPV compliance as correlated to the COVID pandemic, and to identify special-cause variation in LPV compliance throughout the pandemic. The following rules to look for trends and shifts will be employed (5):

- 1 point is outside the control limits.
- 2 out of 3 consecutive points are more than 2 sigmas from the center line in the same direction.
- 4 out of 5 consecutive points are more than 1 sigma from the center line in the same direction.
- 8/9 points on the same side of the center line.
- 6 consecutive points are steadily increasing or decreasing.
- 14 consecutive points are alternating up and down.
- 15 consecutive points are within 1 sigma of the center line.
- 8 consecutive points on either side of the center line with not within 1 sigma.

Part III: Predictors of compliance to LPV

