- We will use a multivariate logistic regression model to determine the independent predictors of LPV use. Predictors with a $p < 0.2$ in the bivariate analysis will be incorporated into model construction. A conservatively high cut-off for the p-value was chosen to minimize type II error (exclusion of a predictor that would have become significant if adjusted for other predictors in the multivariate model). For the same reason, we will not adjust the p-value for multiple comparisons during the predictor screening phase.
- For face validity, we will include age, sex, height, obesity status, night or weekend shift, hospital site, laparoscopic surgery, and pre-COVID era vs. COVID era in the model regardless of bivariate analysis results.
- We will add candidate predictors that passed the bivariate phase in a forward selection method, minimizing the Akaike Information Criterion (3), which rewards improved goodness of fit while simultaneously penalizes over-fitting.
- Pairwise interaction among included terms will be investigated via adding an interaction term for each pair, and comparing the model with and without the interaction term via a likelihood ratio test. A $p < 0.05$ will result in inclusion of that interaction term. As before, to minimize type II error, the p value will not be adjusted for multiple comparison at this stage.
- Finally, the odds ratio of each predictor for LPV use in the final model will be presented with and without Bon Ferroni adjustment for multiple comparisons. A separate result will be presented for interactions, if any are detected.

Sensitivity analyses, subgroup analyses, and other supplemental analyses

- Part I: none planned
- Part II:
 - Subgroup analysis for: academic hospital sites, laparoscopic surgery.
 - Subgroup analysis for patients who would not have met LPV criteria if ventilated by default ventilator settings for tidal volume. This analysis explores whether clinicians became more likely to adjust the ventilator settings intentionally to achieve LPV.
- Part III:
 - We will adjust the date cut-offs for pre-COVID era vs. COVID era based on Shewhart chart results of Part II (i.e. the dates that the Shewhart chart indicated shifts in practice pattern)
 - Subgroup analysis for academic hospital sites only.

8. Ethical considerations

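### The Part II subgroup on intentional ventilator adjustment is selected on tidal volume alone but judged by composite LPV compliance, an imperfect proxy for adjustment, while the extracted set tidal volume goes unused (minor)

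*Combined protocol and SAP*

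**What the plan says.** Section 7, under sensitivity and subgroup analyses for Part II, plans a "Subgroup analysis for patients who would not have met LPV criteria if ventilated by default ventilator settings for tidal volume". Its purpose follows: "This analysis explores whether clinicians became more likely to adjust the ventilator settings intentionally to achieve LPV". No adjustment variable is defined. The only outcome named for Part II is the monthly p chart of LPV compliance.

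Compliance is defined in section 6 (physiologic and therapy data). A patient is compliant if "their average tidal volume was 6-8 mL/kg IBW and their average PEEP throughout the case was as least 5 cm" H₂O. Section 4 makes both parts necessary: "Patients ventilated according to one or neither of the above criteria will not be considered to have been ventilated according to the guidelines". The volume scored is the measured one: "Measured average tidal volume will be compared to LPV tidal volume based on IBW as calculated by the patient’s height".

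Two further statements matter. Section 6 lists what is extracted: "The primary variables of interest include respiratory rate, set and exhaled tidal volume, peak pressure, PEEP". So the set volume is available. Section 7, Part I, gives the current default PEEP as off, since it models the gain in compliance "if the default PEEP setting on anesthesia machines were changed from PEEP = off to PEEP = 5". The default tidal volume is not stated; Part I only plots volumes from 400 to 600 mL.

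**The concern.** Entry and outcome measure different things. Entry asks whether a setting, the default tidal volume, lies outside 6-8 mL/kg IBW. It must refer to the volume criterion only: with default PEEP off, no patient left at all the defaults would meet the full definition. The outcome asks whether a measurement, the case-mean volume, lies inside the same limits, and also whether mean PEEP reached 5. The difference is then read as intent to adjust.

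That reading can fail in three ways:

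- The volume was left at a default just outside the limit, the measured mean drifts inside, and PEEP was raised. The case counts as compliant although the volume setting never moved.
- The volume was moved correctly into range but mean PEEP stayed below 5. The case counts as no response.
- Use of PEEP changes over time while volume practice does not. The chart moves, in a subgroup chosen only for its tidal volume.

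At stake is the interpretation of one supplemental chart: whether a rise in it can be described as clinicians adjusting tidal volume on purpose. The overall compliance rate, the main p chart and the predictor model are not affected.

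**Working it through.** The plan gives no figure for this subgroup, so there is none to reproduce.

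**Inputs from the documents.** Devine IBW (section 6): 50 kg (men) or 45.5 kg (women) + 2.3 × (height in inches − 60). Range 6-8 mL/kg. PEEP criterion of at least 5. Default PEEP off. About 100,000 cases over 120 months.

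**Assumptions, not in the documents.** Default volume 400-600 mL (the span of the Part I plot). 55% women. Height 162 cm (SD 7) in women and 175 cm (SD 7.5) in men. Measured mean volume differs from set volume with SD 5% and no bias.

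**Step 1: single cases, assuming a 500 mL default.**
- Woman, 170 cm: IBW = 45.5 + 2.3 × (66.93 − 60) = 61.4 kg. 500/61.4 = 8.14, so she enters the subgroup. A measured mean of 490 mL gives 7.98, in range with the setting unchanged. She is compliant only if mean PEEP is also at least 5; with PEEP left off she is not.
- Woman, 160 cm: IBW = 45.5 + 2.3 × (62.99 − 60) = 52.4 kg. 500/52.4 = 9.5, so she enters. Set volume changed to 400 mL gives 400/52.4 = 7.6, in range. With mean PEEP below 5 she is scored non-compliant despite the volume change.

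**Step 2: share in range on volume with the setting untouched.** Simulation of 1,000,000 patients. Subgroup: default/IBW below 6 or above 8. In range: default × (1 + 0.05 × Z)/IBW between 6 and 8, with Z standard normal. The last two columns multiply by an assumed 30% or 50% with PEEP of at least 5.

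| Default (mL) | Subgroup, % of patients | In range, setting untouched, % of subgroup | × 0.30 | × 0.50 |
|---|---|---|---|---|
| 400 | 47.5 | 12.6 | 3.8 | 6.3 |
| 450 | 46.7 | 13.7 | 4.1 | 6.9 |
| 500 | 56.4 | 7.3 | 2.2 | 3.7 |
| 550 | 72.4 | 5.3 | 1.6 | 2.7 |
| 600 | 88.6 | 4.2 | 1.3 | 2.1 |

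With bias from −5% to +5% and SD from 3% to 10%, the volume-only share runs from 0.1% to 30%.

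**Step 3: PEEP alone.** Suppose 40% of the subgroup has volume in range throughout, independently of PEEP. If the share with PEEP of at least 5 goes from 30% to 60%, composite compliance goes from 0.40 × 0.30 = 12% to 0.40 × 0.60 = 24%, with no change in volume practice.

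**Step 4: effect on a trend.** Observed proportion = true × sensitivity + (1 − true) × false-positive share. With sensitivity 0.80 and false-positive share 0.10, a true rise from 0.30 to 0.40 shows as 0.24 + 0.07 = 0.31 to 0.32 + 0.06 = 0.38: 7 points instead of 10. With no true change, the observed change is zero.

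**The case against.** The strongest reply is that the outcome suits the stated aim. The aim speaks of ventilator settings and of achieving LPV, and LPV is the composite. A case left wholly at default has PEEP off and is non-compliant, so the drift in step 1 produces a responder only where PEEP was raised, itself an adjustment of a setting. This largely stands. A reader might infer that untouched cases near the limit count as adjusted; under the plan's endpoint they do not. What remains is that selection is on tidal volume alone, which makes sense only if the question is about tidal volume, and the composite cannot show which setting moved.

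A reader might also infer that most modest volume changes are missed. The documents do not support that. In the simulation, a 50 mL change toward the range reaches it in 70%, 67%, 37%, 24% and 18% of the subgroup at defaults of 400, 450, 500, 550 and 600 mL, so the answer reverses with a default that is not stated. A change that stops short also did not achieve LPV, which is what the plan asks about.

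Nor would dilution flatten the chart. At a 500 mL default the subgroup has about 100,000/120 × 0.564 = 470 cases a month. Among patients whose default is too high, 36% reach range with a 50 mL reduction, so a 10-point rise in such reductions shows as about 3.6 points. In simulated charts, a sustained 3.6-point rise from mid-2020 was flagged in at least 99% of runs using only two of the plan's eight rules (false-signal rate 9-13%). At 1.8 points it was flagged in 73-98%. A short-lived shift would be harder to see. A drift in set-versus-measured agreement over the decade is possible, but nothing in the documents suggests one.

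It can also be said that a set-volume measure needs the default volume, which is not given. The subgroup's own entry rule already needs it, so this adds no burden.

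**Conclusion.** The point holds as a minor one. Composite compliance in this subgroup is an imperfect proxy for intentional tidal-volume adjustment: it mixes in PEEP, it can credit an unmoved volume setting near the limit where PEEP was raised, and it gives no credit for a correct volume change without PEEP. The set volume, the direct evidence of adjustment, is extracted but has no role here.

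The size is uncertain. About 4-14% of the subgroup would be in range on volume with the setting untouched, before multiplying by the share with PEEP of at least 5. This rests on the assumed heights and sex mix, a 5% SD without bias and defaults of 400-600 mL; none of the percentages comes from the documents alone. Stable misclassification shrinks the apparent shift and does not manufacture one. The chart is still usable as a record of LPV achieved; what it lacks is the step from that result to intent.

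**What to change.** State in the SAP the default tidal volume or volumes used for subgroup entry, by site and period if they differ.

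Within the subgroup, present three monthly proportions separately:

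- set tidal volume different from the default, toward the patient's 6-8 mL/kg IBW range, by at least a margin stated in advance (the measure of adjustment);
- measured mean tidal volume in range (the result achieved on volume);
- mean PEEP of at least 5.

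The first is a new p chart; the other two split the composite already planned. Put cases without a recorded set volume in a separate row, since ventilation mode is not in the dataset and cannot explain the gap.

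The cost is SAP wording, one derived variable from data already extracted, and an extra chart in an exploratory subgroup. The margin is a judgement and should be fixed before the data are examined. Because section 6 extracts values as case averages, the set volume will also be an average; a setting changed partway through a case will show as a smaller departure from default, which bears on the choice of margin.

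### In the Part II subgroup selected on default tidal volume, a chart of composite compliance cannot show whether a shift came from tidal volume or from PEEP

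*Combined protocol and SAP*

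**What the plan says.** Section 4 (Research objectives and hypothesis) makes the outcome a composite: "Compliance with ventilation guidelines is defined as meeting two criteria", namely average tidal volume of 6-8 mL/kg ideal body weight (IBW) and average PEEP of at least 5 cm H2O. Partial success does not count: "Patients ventilated according to one or neither of the above criteria will not be considered to have been ventilated according to the guidelines".

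Section 7, Part II, plots that outcome over time: "A Shewhart control chart (p chart) of LPV compliance each month will be presented".

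The supplemental analyses for Part II in section 7 then add this one: "Subgroup analysis for patients who would not have met LPV criteria if ventilated by default ventilator settings for tidal volume". The purpose follows at once: "This analysis explores whether clinicians became more likely to adjust the ventilator settings intentionally to achieve LPV". The selection uses tidal volume only, and no other outcome is named, so the composite p chart applies by default.

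Two parts of section 7, Part I, bear on this. Non-compliance is to be split into low PEEP, tidal volume too low or too high, and both, but pooled over the whole period and not within this subgroup. The present PEEP default is described as off, since the plan will model compliance "if the default PEEP setting on anesthesia machines were changed from PEEP = off to PEEP = 5".

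**The concern.** Selecting on default tidal volume isolates patients who need a tidal-volume change if they are to be compliant. It does nothing to isolate PEEP adjustment: with the PEEP default at off, a case left at that default would be expected to fail the PEEP criterion whatever the patient's height. The selection is therefore informative mainly about tidal volume, while the charted outcome mixes tidal volume with PEEP.

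Two errors of interpretation follow. If PEEP use rises among cases whose tidal volume is already in range, the subgroup chart rises although tidal-volume practice has not changed. If clinicians start to tailor tidal volume but leave PEEP below 5, the chart may not move although the behaviour that the subgroup was selected to reveal has changed. What is at stake is the interpretation of this one supplemental analysis, and any educational message about tidal volume drawn from it.

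**Working it through.** The plan gives no figure for this subgroup, so there is none to reproduce. The check is the algebra of the composite, followed by an illustration.

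**Inputs from the documents**
- About 100,000 cases (section 5) from January 2014 to December 2023, which is 120 months: 100,000 / 120 = 833 cases a month.
- Outcome: both criteria must be met (section 4). Chart: monthly p chart (section 7, Part II).
- Default PEEP: off. Default tidal volume: not stated. Part I gives only the range to be plotted ("for tidal volumes from 400-600mL"), so the size of the subgroup cannot be derived.

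**Assumed inputs**
- q = share of the subgroup with tidal volume in range.
- r = share of those in-range cases with PEEP of at least 5.
- n = subgroup cases a month. n = 400 is a share of 400 / 833 = 48%.

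**Step 1, identity.** Composite compliance p = q x r. Because r is conditional on tidal volume being in range, no independence assumption is needed. One series p cannot identify q and r separately.

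**Step 2, single case.** A case left at its out-of-range default tidal volume is non-compliant whatever its PEEP: with q = 0, p = 0 for every r. The ambiguity therefore lies in the monthly proportion and arises through cases already in range.

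**Step 3, PEEP rises and q stays fixed.** Take q = 30%, r from 30% to 50%, n = 400.
- p goes from 0.30 x 0.30 = 9% to 0.30 x 0.50 = 15%.
- Centre line frozen at baseline: sigma = sqrt(0.09 x 0.91 / 400) = 0.0143, and 0.06 / 0.0143 = 4.2 sigma.
- Whole-period centre line, assuming 75 months before and 45 after the shift: centre = (75 x 9% + 45 x 15%) / 120 = 11.25%; sigma = sqrt(0.1125 x 0.8875 / 400) = 0.0158; (0.15 - 0.1125) / 0.0158 = 2.4 sigma.

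With q = 50% instead, p goes from 15% to 25%: 0.10 / sqrt(0.15 x 0.85 / 400) = 5.6 sigma from the frozen line. The whole-period centre is 18.75%, sigma is 0.0195, and the later months sit 0.0625 / 0.0195 = 3.2 sigma out.

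**Step 4, range.** This uses the normal approximation and an upper limit of p + 3 sqrt(p(1 - p) / n) frozen at baseline.
- Subgroup share 40% (n = 333), q = 40%, r from 30% to 60%: p goes from 12% to 24% against a limit of 17.3%. The chance that a given month exceeds it is about 99.8%.
- Same share and change in r, q = 10%: 3% to 6% against a limit of 5.8%, about 56% a month.
- Shares of 20-60%, q of 10-60%, and r from 30% to 50%, 30% to 60% or 50% to 70%: from about 6% to nearly 100% a month.

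These are chances for the single-point rule only. The run rules in Part II can also flag smaller sustained shifts.

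**Step 5, the converse.** Let q rise from 30% to 60%.
- If r stays at 30%, p goes from 9% to 18%, so a 30-point change appears as 9 points.
- If every newly in-range case has PEEP below 5, r falls from 30% to 15% and p = 0.60 x 0.15 = 9%: no movement at all.

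A chart of q would show 30% to 60% in both situations, and a flat line in Step 3.

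**The case against.** The strongest reply is that the stated purpose refers to ventilator settings in general and not to tidal volume. LPV is defined by both criteria and the PEEP default is off, so turning PEEP on is itself an adjustment towards LPV. On that reading the composite suits the aim. This stands, and it limits the point. A reader might infer that the subgroup cannot support its stated conclusion, or that PEEP alone could make these patients compliant. The documents support neither: the purpose is worded broadly, and a case left at the failing default tidal volume stays non-compliant. What remains is that the selection rule has a clear rationale only for tidal volume, and the composite cannot show which component moved.

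It can also be said that a non-deliberate rise in PEEP is speculative, since the plan treats a new PEEP default as hypothetical and reports no such change during the study. That is fair, but the ambiguity needs no default change; any rise in PEEP use among in-range cases produces it.

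The sigma figures rest on assumed q, r and n and on an unstated choice of centre line. That also stands, which is why both versions and a range are shown.

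Finally, a tidal-volume chart would not prove intent, because section 7, Part III, notes that ventilation mode is not recorded. This is correct. Component charts remove the confusion between components, not the uncertainty about motive.

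**Conclusion.** The point holds in limited form. With the composite as its only, and merely implied, outcome, this subgroup's monthly chart cannot attribute a shift to tidal volume or to PEEP, and it can mislead in either direction. That follows from p = q x r and needs no assumed numbers.

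The size does depend on assumptions. In the main illustration a PEEP-only change takes compliance from 9% to 15%, about 4.2 sigma or 2.4 sigma according to the centre line, with q unchanged. With few in-range cases and a small subgroup, a single month would rarely cross the limit.

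The pooled breakdown in Part I does not resolve this, because it is neither monthly nor restricted to the subgroup. The consequence is confined to a supplemental analysis. The primary compliance rate and the main predictor model do not depend on it.

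**What to change.** In the Part II supplemental analyses, name the outcomes for this subgroup and add two monthly p charts beside the composite: the tidal-volume criterion (average 6-8 mL/kg IBW, yes or no) and the PEEP criterion (average at least 5 cm H2O, yes or no). State that any conclusion about tidal-volume adjustment will rest on the tidal-volume chart, and that the composite describes LPV overall. Say how the centre line is set, and record the machine default tidal volume used to define the subgroup, since the documents do not give it.

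Both components are already derived for Part I, so no new data are needed. The cost is two more charts and the additional chance signals that come from applying the same run rules to them. Describing these charts as exploratory is enough to deal with that.

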The primary hypothesis is that not all patients will be ventilated according to the recommended LPV strategy. We further hypothesize that patient height will be a major predictor in determining compliance to LPV, as our clinical experience suggests that while IBW used to set tidal volumes is calculated based on height, many anesthesiologists set tidal volumes by actual weight rather than IBW. Therefore, this practice may result in tidal volumes outside of a patient's acceptable tidal volume as would be recommended by LPV guidelines. Our other hypothesized predictors to LPV compliance include predictors that indicate respiratory dysfunction (e.g. severe COPD, CHF) or severe illness (American Society of Anesthesiologists [ASA] classification, sepsis), as anesthesiologists may be more cognizant of the need for LPV in these patients. Lastly, we hypothesize that the COVID pandemic will introduce a shift towards increased LPV compliance, but this shift may not be sustained in the post-pandemic era as precautions waned.

5. Methods

Study design

Our study is a retrospective cohort study investigating the correlation between hypothesized predictors of LPV compliance and actual LPV practice in a large multi-center health authority. The study population is all patients who underwent a general anesthetic for any procedure at a Fraser Health Authority hospital from January 2014 – December 2023. See Section 7 for more details regarding inclusion and exclusion criteria.

Sampling and sample description

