- Our list of hypothesized predictors to LPV use include:
 - Age
 - sex
 - height
 - obesity (body mass index > 30)
 - elective/emergency
 - ASA Class
 - sepsis
 - functional health status
 - anesthesia duration
 - dyspnea
 - severe COPD
 - CHF
 - smoker
 - surgical specialty
 - ventilatory dependent
 - Pre-COVID era vs. COVID era
 - Night or weekend shift (1)
 - Hospital site
 - Use of neuromuscular blockade
 - Presence of epidural anesthesia
 - Inpatient vs. outpatients
 - Laparoscopic surgery
 - Transfusion of blood products
 - Dialysis
 - Ascites
 - NB: We considered before January 2020 as the pre-COVID era, and after June 2020 as the COVID era. The former cutoff was chosen as January 2020 contained the first COVID case in BC. The latter cutoff was chosen as it constitutes three months after March 2020, when the World Health Organization announced COVID's pandemic status, and BC announced a state of emergency with the start of isolation policies. We hypothesized that any impact of the COVID pandemic on LPV compliance patterns would unlikely to have occurred prior COVID's arrival in BC, but would likely be in full swing three months after initiation of widespread social isolation, a very palpable event in society.
 - NB2: parameters such as oxygen saturation, end-tidal carbon dioxide, and peak inspiratory pressures may be affected by use of LPV, and therefore will not be included as candidate predictors due to high likelihood of reverse causation (2). Mode of ventilation has been shown to correlate with LPV compliance(2), but this is unfortunately not recorded in our dataset.
- To screen for inclusion in the multivariate logistic regression model, the association of each hypothesized predictor to LPV use will be first explored using bivariate analyses.

Chi squared test will be used for categorical hypothesized predictors (or Fisher's exact test if a covariate pattern results in < 5 cases). Bivariate logistic regression (including only the predictor and LPV) will be used for continuous hypothesized predictors.

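### The Part III sensitivity analysis dates the COVID era from the outcome series it then tests, so its nominal p-value and confidence interval are not valid

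*Combined protocol and SAP*

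**What the plan says.** Section 7, Part II: "A Shewhart control chart (p chart) of LPV compliance each month will be presented", with eight rules for detecting special-cause variation.

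Section 7, Part III: "We will use a multivariate logistic regression model to determine the independent predictors of LPV use". The terms forced into that model include "pre-COVID era vs. COVID era in the model regardless of bivariate analysis results". The first note under the predictor list fixes the main dates: "We considered before January 2020 as the pre-COVID era, and after June 2020 as the COVID era". It justifies them by outside events, namely the first provincial case, the pandemic declaration and the provincial emergency. Of the second date it says: "The latter cutoff was chosen as it constitutes three months after March 2020".

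Section 7, sensitivity analyses, Part III: "We will adjust the date cut-offs for pre-COVID era vs. COVID era based on Shewhart chart results of Part II", explained as "the dates that the Shewhart chart indicated shifts in practice pattern".

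The plan does not say which of the eight rules counts as a shift, which signal applies if there are several, or what happens if there is none. Bonferroni adjustment is offered for multiple comparisons in the final model. Nothing is said about the choice of dates.

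**The concern.** The chart and the regression use the same patients and the same outcome. Placing the era boundary where the compliance series appears to move, and then testing whether compliance differs across it, uses the data twice. The standard p-value and interval assume a boundary chosen without sight of the outcome.

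Whether COVID shifted compliance is an objective and a hypothesis of the study (Section 4). A chart-dated odds ratio printed beside the fixed-date one, with its own p-value, is likely to be read as corroboration. A check of robustness to the choice of dates should vary the dates for reasons unrelated to the result.

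**Working it through.** The documents give no alpha for the era odds ratio and no power calculation, so there is no planned figure to reproduce. The question is how often the chart-dated test rejects when there is no era effect.

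**Inputs from the documents**
- Study window (Section 5): "any procedure at a Fraser Health Authority hospital from January 2014 – December 2023", which is 10 × 12 = 120 months.
- Main eras: 72 months before January 2020 and 42 months after June 2020. The 6 months between belong to neither (72 + 6 + 42 = 120).
- About 100,000 cases (Sections 5 and 9): 100,000 / 120 ≈ 833 per month. The main comparison is then 72 × 833 = 59,976 against 42 × 833 = 34,986 cases.

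**Assumptions**
- Cases are spread evenly over months.
- Two-sided alpha is 0.05.
- Baseline compliance is 20%, 40% or 60%. The background says only that compliance is under 50% elsewhere.
- There are no covariates and no site clustering.
- The chart sets a single before/after date. If nothing signals, the fixed dates are kept.

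**Formulas**
- Chart: z_m = (p_m − p̄) / √[p̄(1 − p̄)/833]. At 40%, one sigma is √(0.24/833) = 0.017, so the control limits are about ±5.1 points.
- Dates come from five shift or trend rules: beyond 3 sigma, 2 of 3, 4 of 5, 8 on one side, and 6 rising or falling.
- Era test: z = (p₁ − p₂) / √[p̄(1 − p̄)(1/n₁ + 1/n₂)], rejecting if |z| > 1.96.
- 3,000 series per baseline rate. Monte Carlo standard error is √(0.05 × 0.95/3,000) = 0.4 points.

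**Check of the set-up.** At 40% with fixed dates, SE(log OR) = √[(1/0.24)(1/59,976 + 1/34,986)] = 0.0137. The expected mean absolute log OR under the null is √(2/π) × 0.0137 = 0.011, and the simulation gave 0.011.

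**Type I error with no era effect, over the three baseline rates**

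| How the date is set | Rejects |
|---|---|
| Fixed dates as planned | 4.5–5.4% |
| First signal from January 2020 | 7.6–8.7% |
| Signal nearest pandemic onset | 7.6–8.3% |
| Strongest signal in 2019–2022 | 8.4–9.6% |
| Strongest signal at any date | 12.9–13.8% |

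The coding of the rules matters. Taking the first signal from January 2020 under the first four rules, at 30% baseline, gave 6.4%. Dating the shift at the month in which the rule completes gave 4.5%, which is no excess. The range is therefore roughly 5% to 14%.

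False signals are common. At least one of the eight rules fired in 80–82% of null series. Among 4,000 null series at 40%, 1,861 (46.5%) had a shift or trend signal in 2019–2022. In those series fixed dates rejected 7%, the first or nearest signal 11%, and the strongest 15%.

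**Size of the bias.** Under the null at 40%, mean absolute log OR rises from 0.011 to 0.013–0.018. With a real step in April 2020:
- True log OR 0.05: chart-dated estimates averaged 0.045–0.051.
- True log OR 0.20: chart-dated estimates averaged 0.196–0.200.

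**The case against.** The strongest defence is that this is one supplemental run. The main era estimate uses dates fixed in advance for outside reasons, no decision depends on the chart-dated model, and readers will see both odds ratios and the chart. That stands, and it limits the consequence. It does not make the nominal p-value valid.

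A second defence is that the chart-dated run asks a fair question: did the assumed dates misplace when practice changed? Alternative cut-offs in early 2020 would miss a later shift, or the later decline that Section 4 anticipates. This also stands, and is why the run should be kept as description.

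Three stronger readings are tempting, and the documents do not support them.
- *That the analysis can only confirm or strengthen the main result.* With the date at the first signal from January 2020 (30% baseline), the chart-dated odds ratio was closer to 1 than the fixed-date one, or reversed, in 43% of signalled null series. The share was 43% with a real 1-point step and 61% with a 3-point step.
- *That the error rate exceeds 20%.* Searching every cut from January 2020 to December 2022 for the most extreme one gives about 21–22%, or 36–37% with 1 point of extra monthly SD. The plan describes no such search. With that extra SD the fixed dates already reject 10%, so part of the rise is overdispersion. Rates of 58–75% arise only if the era is shrunk to the flagged months and only signalled series are counted. The plan speaks of adjusting cut-off dates, not of that.
- *That the effect is inflated in general.* Inflation is seen mainly at or near the null.

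**Conclusion.** The concern holds. The chart-dated odds ratio carries a p-value and interval that ignore how its dates were chosen, and it is not independent evidence of a COVID effect. With no true effect, type I error lies between roughly 5% and 14% against a nominal 5%, according to a selection rule the plan leaves open.

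The mechanism is certain from the text. The figures are conditional on the assumptions listed above and on no month-to-month variation beyond binomial. With extra variation (SD 0.1 on the logit scale, 40% baseline), the fixed-date test itself rejects 27%, the first or nearest signal 28–29%, and the strongest-signal rules 66–90%. Overdispersion is thus a separate problem that also makes a strongest-signal rule much worse.

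**What to change.** Amend the Part III sensitivity paragraph in three ways.

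1. Make the robustness check one or more alternative cut-offs fixed now from dates the Part III note already names (January, March or June 2020), for example before and after March 2020.
2. Keep the chart-dated model only as an exploratory, descriptive result, labelled as such. State in advance which rule and which signal set the date, whether that is the start of the run or the month the rule completes, and what is done if there are several signals or none.
3. Report it without a nominal p-value, or with one from a permutation that repeats the whole sequence of chart, rules, date selection and model. Permuting whole months would keep any extra monthly variation, but assumes months are exchangeable under the null. Any interval shown should carry a note that it ignores the date selection.

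The cost is SAP wording, plus modest programming if the permutation is chosen. No data and no main analysis change. The downside is that the chart-dated odds ratio loses its nominal p-value.
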